9.2. Setting

The study cohort will include patients aged 40-59 years who were firstly diagnosed with menopausal symptoms and initiated MHT between January 1, 2012 and December 31, 2019. Patients with menopausal symptoms will be defined as at least one inpatient or outpatient claim with any of the following diagnosis codes (Table 1), restricted to primary and secondary diagnosis. The cohort entry date will be defined as the date of first diagnosis of menopausal symptoms and the index date will be defined as the date of the first prescription for MHT.

The exclusion assessment window will be defined as the year before the index date. Patients meeting any of the following criteria will be excluded: 1) patients diagnosed with breast cancer (C50, D05), endometrial cancer (C54.1), or granulosa cell tumor (C56); 2) patients diagnosed with coronary heart disease (I20-I25, I51.6), stroke (I60-64), or VTE (I80.2, I80.3 I26); 3) Patients diagnosed with viral hepatitis (B16-B19), cirrhosis (K70.2-K70.4, K71.7, K72.0-K72.1, K72.9, K74.0-K74.6, K76.1, K76.6-K76.7, R18, I85.0, I85.9, I86.4, I86.8, I98.2-I98.3), and hepatic cancer (C22); 4) patients diagnosed with gallbladder disease (K80, K81, K82, K83, K85.1), gallbladder cancer (C23), extrahepatic bile duct cancer (C24) within 1 year prior to the index date. Baseline characteristics including demographic characteristics, and medical institution type will be assessed on cohort entry date and comorbidities, concomitant medications and proxies of health status will be assessed within 1 year prior to cohort entry date. Menopausal symptoms will be assessed within 90 days after cohort entry date. Type of administration will be assessed on index date. (Figure 1).

PFIZER CONFIDENTIAL

In the identified study cohort, we will examine treatment patterns, adherence, and persistence of MHT during the follow-up window, which will be defined from the index date (date of first prescription for MHT) to the end of the study period (December 31, 2020).

[figure not shown]
[figure not shown]

Figure 1. Study design scheme

[§] Menopausal symptoms: Vasomotor symptoms, Bone and joint symptoms

Figure 2. Study Flowchart

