 - First, we will examine trends by 3 classes of MHT: ET (estrogen therapy), EPT (estrogen-progestin therapy) and tibolone. The time-series trend will be presented as the proportion of each class of MHT quarterly, calculated as the number of patients receiving each class of MHT divided by the total number of patients prescribed with MHT.
 - Second, we will examine trends by age group: all, 40-44, 45-49, 50-54, and 55-59. The time-series trend will be presented as the proportion of MHT use by each age group, calculated as the number of patients in each age group divided by the total number of patients prescribed with MHT.
 - Third, we will examine trends by menopausal symptoms: vasomotor symptoms, bone and joint symptoms, genitourinary symptoms, and psychosomatic symptoms. The time-series trend will be presented as the proportion of MHT use by each menopausal symptom, calculated as the

number of patients with each menopausal symptom divided by the total number of patients prescribed with MHT.

- Fourth, we will examine trends by the type of administration: systemic HT (oral), systemic HT (transdermal) and local HT (transvaginal). The type of administration of MHT will be classified as follows (Table 4). The time-series trend will be presented as the proportion of MHT use by each type of administration, calculated as the number of patients with MHT by each type of administration divided by the total number of patients prescribed with MHT.

Table 4. Type of administrations

Type of administrations	Ingredient code
Systemic HT (oral)	All ingredient codes except those for systemic HT (transdermal) and local HT (transvaginal)
Systemic HT (transdermal)	154902CCM 154904CPC 154905CPC 154906CPC 154907CSI 154908CCM 154908COM 154930CCM 154931CCM 154932CCM 154601CPC 154602CPC 154603CPC 154604CPC 154605CPC 154606CPC 335900CPC 336000CPC

Local HT (transvaginal)	155303CCM 155402CCM 155430CCM 155201CCM 155202CSP 507700CTB 336200CTB 155502CCM 219001CCS 219001CCM 219030CCM 336100CTB
-------------------------	--

4) Treatment regimens change of MHT across time

- We will depict treatment switch and discontinuation patterns across time by measuring the number of different treatments, including ET, EPT and tibolone, at time points of 3, 6, 9, and 12 months from the index date. Switching and discontinuation of MHT across time will be presented with a Sankey diagram.

5) Time to switch and discontinuation of MHT

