9.7. Data analysis

We will investigate the baseline characteristics of patients with MHT. Baseline characteristics such as age, insurance type and income levels, and medical institution type will be assessed on cohort entry date. Baseline characteristics such as CCI, no. of outpatient visits/hospitalization, comorbidities and concomitant medications will be assessed on during a 1-year period before cohort entry date. Type of administration will be assessed on index date. The results will be presented in frequency (proportion) for categorical variables and mean (SD) or median (IQR) for continuous variables.

All outcome variables will be summarized descriptively through the tabular or graphical form of means, medians, ranges, and standard deviations of continuous variables and frequency distributions of categorical variables.

Annual time-series prevalence of menopausal symptoms and use of MHT will separately be calculated among total women aged 40-59.

The prevalence of each menopausal symptom among patients with MHT will be calculated as the number of patients diagnosed with each menopausal symptom divided by the number of patients diagnosed and prescribed for MHT. Menopausal symptoms, assessed within 90 days after the cohort entry date, will be classified into 4 categories: vasomotor symptoms, bone and joint symptoms, genitourinary symptoms, and psychosomatic symptoms.

We will examine annual and quarter time-series trends in the prevalence of use for MHT by treatment class, age group, menopausal symptoms, and the type of administration between 2012 and 2020.

We will examine annual and quarterly time-series trends in the prevalence of MHT use by 3 types of MHT: ET (estrogen therapy), EPT (estrogen-progestin therapy), and tibolone. The time-series trend will be presented as the proportion of each type of MHT quarterly, calculated as the number of patients receiving each type of MHT divided by the total number of patients prescribed with MHT.

We will examine annual time-series trends in the prevalence of MHT use by age group: all ages, 40-44, 45-49, 50-54, and 55-59. The time-series trend will be presented as the proportion of MHT use by each age group, calculated as the number of patients in each age group divided by the total number of patients prescribed with MHT.

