We will examine annual time-series trends in the prevalence of use for MHT by menopausal symptoms: vasomotor symptoms, bone and joint symptoms, genitourinary symptoms, and psychosomatic symptoms. The time-series trend will be presented as the proportion of MHT use by each menopausal symptom, calculated as the number of patients with each menopausal symptom divided by the total number of patients prescribed with MHT.

We will examine annual time-series trends in the prevalence of use for MHT by the type of administration: systemic HT (oral), systemic HT (transdermal) and local HT (transvaginal). The time-series trend will be presented as the proportion of MHT use by each type of administration, calculated as the number of patients with MHT by each type of administration divided by the total number of patients prescribed with MHT.

Switching and discontinuation of MHT for any other MTH type will be shown by using Kaplan-Meier curve. Discontinuation will be defined as no subsequent prescriptions within 2 months of last prescription date. We will conduct a sensitivity analysis where discontinuation of MHT is defined as a 4-month period without any MHT.

Treatment persistence is calculated by the average length of treatment of the drugs that were prescribed at the index date. Treatment adherence will be shown by calculating MPR (medication possession ratio), calculated as a total number of days of supply of medication divided by the number of days of the follow-up period.

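### Symptom category is read only in the 90 days after first diagnosis, yet it describes MHT patients whose treatment may start up to 7.75 years after that window closes

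*Combined protocol and SAP*

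**What the plan says.** Section 9.2 sets two anchor dates. For entry: "The cohort entry date will be defined as the date of first diagnosis of menopausal symptoms". For treatment: "the index date will be defined as the date of the first prescription for MHT". The cohort is women aged 40-59 "firstly diagnosed with menopausal symptoms and initiated MHT between January 1, 2012 and December 31, 2019". Nothing limits the interval between the two dates.

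Symptoms are tied to the first anchor: "Menopausal symptoms will be assessed within 90 days after cohort entry date". Section 9.7 repeats this in the paragraph on symptom prevalence among MHT patients: "Menopausal symptoms, assessed within 90 days after the cohort entry date, will be classified into 4 categories".

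On trends, section 9.7 says: "We will examine annual and quarter time-series trends in the prevalence of use for MHT by treatment class, age group, menopausal symptoms", together with type of administration, for 2012 to 2020. By symptom, the measure in section 9.3.2 is the "number of patients with each menopausal symptom divided by the total number of patients prescribed with MHT", and section 9.7 repeats the formula. Neither trend paragraph names a symptom window. The abstract places these yearly calculations within the final study cohort.

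Other variables do use the index date. Type of administration is taken on it, and the exclusion criteria look back one year from it.

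**The concern.** Objective 1 asks for MHT prevalence by menopausal symptom. A reader of that result will take the symptom to be one present around the time of treatment. Under the stated window it is the symptom coded around the first menopausal diagnosis, however long before treatment that was.

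Table 1 allows entry on an osteopenia or osteoporosis code alone. A woman who enters on such a code in 2012, is first coded with vasomotor symptoms in 2018 and then starts MHT would appear among MHT patients as bone and joint, and not as vasomotor. At stake are the symptom profile of MHT patients and the reading of any change in that profile over calendar time.

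**Working it through.** The plan has no figure of its own on this point. The check uses the stated dates and a comparison of Tables 1 and 3.

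**Inputs.** Diagnosis and MHT initiation both fall between 1 January 2012 and 31 December 2019, the symptom window is entry + 90 days, and the study ends on 31 December 2020 (all section 9.2).

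**Step 1: largest gap from window to MHT start.** Entry on 1 January 2012 + 90 days closes the window on 31 March 2012. From 1 January 2012 to the last permitted index date is 2,921 days. 2,921 - 90 = 2,831 days, and 2,831 / 365.25 = 7.75 years.

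**Step 2: oldest symptom data in the trends, if they use this window.** From 1 January 2012 to 31 December 2020 is 3,287 days. 3,287 - 90 = 3,197 days, or 8.75 years. At the end of 2012 the same woman's window had been closed for only 275 days. The greatest possible age of the symptom data therefore grows along the series.

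**Step 3: the last year.** The latest entry, 31 December 2019, closes its window on 30 March 2020. No woman in the cohort can contribute a symptom code from Q2, Q3 or Q4 2020. By 31 December 2020 even the most recent window has been closed for 276 days.

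**Step 4: entry codes against symptom codes.**

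| Table 3 category | Codes that are also entry codes (Table 1) | Codes that are not |
|---|---|---|
| Vasomotor | N95.1, N95.3, N95.8, N95.9 | R23.2 |
| Bone and joint | M80.0, M81.0, M81.99, M85.99 | none |
| Genitourinary | N95.2 | N94.1, N95.0, F52.6 |
| Psychosomatic | none | F32, F33, F51, G47 |

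Every entry code maps to a category, so each woman is classified by her entry diagnosis if day 0 counts as part of the window. Psychosomatic symptoms count only if a further code is recorded inside the 90 days. A gynaecologist's sleep-disorder code on day 200, with MHT started that day, would not count.

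**Step 5: sensitivity to the unreported gap (illustration only).** Assume an exponential diagnosis-to-MHT gap with median m days, ignoring the cut-off at the end of 2019. The share starting MHT within the window is 1 - 2^(-90/m). The share starting more than a year after it closed is 2^(-455/m), since 365 + 90 = 455.

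| Assumed median (days) | MHT start within window | MHT start > 1 year after window closed |
|---|---|---|
| 7 | about 100% | about 0% |
| 30 | 88% | about 0% |
| 90 | 50% | 3% |
| 180 | 29% | 17% |
| 365 | 16% | 42% |
| 730 | 8% | 65% |

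The problem is small if most women start MHT soon after diagnosis and large if they do not. The protocol does not say which.

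**The case against.** The strongest reply is that anchoring symptoms at cohort entry is a coherent choice. Age, insurance type, institution, comorbidities and concomitant medications are all set at or before that date, and the plan describes patients with MHT without saying that the symptoms are those at MHT initiation. This stands as far as it goes: symptom at first diagnosis is a legitimate quantity. It is not labelled as such, however, and it is not what a reader of Objective 1 would expect.

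Three stronger readings are tempting, and the documents do not support them.

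- *That the plan freezes each woman's category in every trend period.* The trend paragraphs give no symptom window, so this is an inference from its being the only one stated for the cohort. Figure 1, cited for these windows, is not shown and might add detail. The quarterly frequency also comes from the general trend statements; the by-symptom paragraph in section 9.7 mentions only annual trends.
- *That symptoms are mostly picked up on treatment when MHT starts at entry.* Step 4 shows that the entry diagnosis itself supplies a category, contemporaneous with that start. Only additional codes can post-date MHT.
- *That a stated percentage of women is misclassified.* No source in the documents supports one. The four categories are also not declared mutually exclusive, so a later code may add a category without making the first one wrong.

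The 7.75-year gap is the extreme case, and new women enter until the end of 2019. Neither the direction nor the size of any distortion in the trends can be shown from the documents.

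**Conclusion.** The point holds and should be settled before analysis. For symptom prevalence among MHT patients, the 90-day window is explicit in section 9.7 and is not tied to treatment. MHT may start up to 7.75 years after it closes. For the trends, the defect is a missing definition: if the only stated window applies, symptom data can be up to 8.75 years old, and none can come from Q2-Q4 2020. Psychosomatic symptoms are the most exposed category.

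This rests on the stated dates, on the trends being computed within the final cohort as the abstract says, and on day 0 counting within the window. The number of women affected cannot be derived without the diagnosis-to-MHT gap. The annual prevalence of diagnosed symptoms over the mid-year population (outcome 1) is a separate measure and is not affected.

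**What to change.** - For symptom prevalence among MHT patients, assess Table 3 codes in a look-back ending on and including the index date, for example 90 days.
- For the trends, state a symptom window tied to each reporting period, for example a look-back ending at the MHT prescription in that period. Requiring a code in the same quarter would be too strict.
- Allow more than one category per woman. Report women with no code in the window as a separate unclassified group, kept in the denominator.
- Report the distribution of the diagnosis-to-MHT gap.
- Keep the 90-days-after-entry version as a secondary result, labelled as by symptom at first diagnosis.

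**Cost.** Wording changes are needed in sections 9.2, 9.3.2 and 9.7 and in the abstract. One index-date variable and a set of period-specific variables must be derived: 9 years, or up to 9 x 4 = 36 quarters. All come from the 2011-2020 claims already requested, which also cover a 90-day look-back from the earliest index date. The drawback is that some women will be unclassified, and their share should be shown. If the sponsor prefers the present anchor, the minimum is to state the trend window, label the results as by symptom at first diagnosis, and report the gap.

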9.2.1. Inclusion criteria

Patients must meet all of the following inclusion criteria to be eligible for inclusion in the study:

Using the HIRA database, which covers the entire Korean population of ≥ 50 million, we will include patients who meet all the following the inclusion criteria.

1. Patients aged 40-59 years at cohort entry date.
2. Patients who had at least one inpatient or outpatient diagnosis of menopausal symptoms (detailed below) between January 1, 2012 and December 31, 2019.

Table 1. Diagnosis codes for inclusion

KCD-8* code	Description
N95.1	Menopausal and female climacteric states
N95.2	Postmenopausal atrophic vaginitis
N95.3	States associated with artificial menopause
N95.8	Other specified menopausal and perimenopausal disorders
N95.9	Menopausal and perimenopausal disorder, unspecified
M80.0	Postmenopausal osteoporosis with pathological fracture
M81.0	Postmenopausal osteoporosis
M81.99	Osteoporosis, unspecified, site unspecified; Osteopenia

PFIZER CONFIDENTIAL

M85.99	Disorder of bone density and structure, unspecified, site unspecified; Osteopenia, mild; Osteopenia, moderate; Osteopenia, severe
--------	---

*KCD-8 (Korean standard classification of disease, 8th revision): Korean version of ICD-10 (International statistical classification of diseases and related health problems, 10th revision)

9.2.2. Exclusion criteria

1. Patients diagnosed with breast cancer (C50, D05), endometrial cancer (C54.1), and granulosa cell tumor (C56) within 1 year prior to the index date.
2. Patients diagnosed with coronary heart disease (I20-I25, I51.6), stroke (I60-64), and VTE (I80.2, I80.3 I26) within 1 year prior to the index date.
3. Patients diagnosed with viral hepatitis (B16-B19), cirrhosis (K70.2-K70.4, K71.7, K72.0-K72.1, K72.9, K74.0-K74.6, K76.1, K76.6-K76.7, R18, I85.0, I85.9, I86.4, I86.8, I98.2-I98.3), and hepatic cancer (C22) within 1 year prior to the index date.
4. Patients diagnosed with gallbladder disease (K80, K81, K82, K83, K85.1), gallbladder cancer (C23), extrahepatic bile duct cancer (C24) within 1 year prior to the index date.

9.3. Variables

9.3.1 Exposure

As our main goal of this study is to understand current treatment patterns of MHT, exposure will be defined as the medications prescribed most likely to treat menopausal symptoms based on current treatment guideline. We will classify treatment classes of MHT as below:

Table 2. Prescription drugs for inclusion

MHT type	Ingredient	Ingredient code
Estrogen therapy (ET)	Estradiol hemihydrate	154901ATB 154902CCM 154903ATB 154904CPC 154905CPC 154906CPC 154907CSI 154908CCM 154908COM

PFIZER CONFIDENTIAL

		154930CCM 154931CCM 154932CCM
	Estradiol valerate	155001ATB 155002ATB
	Conjugated estrogens	155301ATB 155303CCM 155401ATB 155402ATB 155402CCM 155404ATB 155430CCM
	Estriol	155201CCM 155202CSP
	Estriol/Lactobacillus Acidophilus	507700CTB
	Ethynodiol diacetate	156401ATB
	Estradiol	154601CPC 154602CPC 154603CPC 154604CPC 154605CPC 154606CPC
	Estradiol/Lactobacillus Acidophilus	336200CTB
	Estropipate	155501ATB 155502ATB 155502CCM
	Promestriene	219001CCS 219001CCM 219030CCM 336100CTB
Estrogen + Progestin Therapy (EPT)*	Estradiol hemihydrate/Norethisterone acetate	297000ATB 297100ATB 298200ATB
	Estrodiol or Estradiol hemihydrate/Dydrogesterone	297400ATB 433700ATB 433800ATB
	Estrodiol hemihydrate/Drospirenone	490400ATB
	Estradiol valerate/Norethisterone acetate	507600ATB

	Estradiol valerate/Medroxyprogesterone acetate	297600ATB 297700ATB 433900ATB 434000ATB 434100ATB 441800ATB
	Estradiol valerate/Cyproterone acetate	297800ATB 398400ATB
	Estradiol valerate/Levonorgestrel	297500ATB 298000ATB
	Estradiol valerate/Norgestrel	297900ATB
	Conjugated estrogen/Medroxyprogesterone acetate	297200ATB 297300ATB 298100ATB 424600ATB 424700ATB 424800ATB 424900ATB 453500ATB 465500ATB
	Estradiol/Norethindrone acetate	335900CPC
	Estradiol/Norethistrone acetate	336000CPC
	Dydrogesterone†	150501ATB
	Medroxyprogesterone acetate†	188901ATB 188903ATB 188904ATB 188905ATB 188906ATB
	Micronized progesterone †	195001ACS
	Cyproterone acetate†	139401ATB
	Norethisterone†	203201ATB
Tibolone	Tibolone	239001ATB

*Estrogen and progestin in combination and estrogen monotherapy plus progestin monotherapy will be included.

†Regarding Estrogen monotherapy plus Progestin monotherapy, only both estrogen and progestin within the same prescription will be considered as progestin therapy as progestin therapy is only approved for use in combination with estrogen.

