- Over time since the index date (initiation of MHT), Kaplan-Meier survival curves will be generated to calculate the time to non-persistence events including switch and discontinuation. Discontinuation will be defined as no subsequent prescriptions within 2 months of last prescription date.
- Switching MHT for any other treatment classes. (i.e. Switch will be defined as when a patient initiating a ET is prescribed a tibolone or EPT)

6) Treatment persistence and adherence

- Treatment persistence is calculated by the average length of treatment of the drugs prescribed at the index date. Persistence rate at 3-, 6-, 9-, and 12-month will also be calculated.

- Treatment adherence will be evaluated using medication possession ratio (MPR), calculated as the total number of days of medication supply divided by the number of days in the follow-up period.

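### Table 2 lists ethynodiol diacetate, a progestin, as estrogen therapy and without the dagger, so either the name or the class on that row is wrong and the code needs checking before the data request

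*Combined protocol and SAP*

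**What the plan says.** Section 9.3.1 assigns class by position in Table 2: "We will classify treatment classes of MHT as below". The ET block has ten ingredient rows. Nine name an estrogen product; the tenth is "Ethynodiol diacetate", code 156401ATB, with no footnote mark.

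Two footnotes govern progestins in Table 2:

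- The asterisk, on the EPT block: "Estrogen and progestin in combination and estrogen monotherapy plus progestin monotherapy will be included".
- The dagger, on dydrogesterone, medroxyprogesterone acetate, micronized progesterone, cyproterone acetate and norethisterone: "only both estrogen and progestin within the same prescription will be considered as progestin therapy". The reason given is that progestin is approved only alongside an estrogen.

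Three other rules use the table. In Section 9.2, "the index date will be defined as the date of the first prescription for MHT". In Section 9.3.2, Table 4 defines the oral route by exclusion: any code in neither the transdermal nor the transvaginal list is oral. Also in Section 9.3.2, "Switch will be defined as when a patient initiating a ET is prescribed a tibolone or EPT".

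Nothing elsewhere in the protocol explains or corrects the ethynodiol diacetate row.

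**The concern.** A progestin sitting in the ET block escapes the safeguard that the protocol applies to every other stand-alone progestin. If the name on the row is right, a woman who receives only this drug, with no estrogen, can enter the cohort as an ET initiator. Her index date then fixes her exclusion window and the start of her follow-up. If she later receives an estrogen-progestin product, the analysis would record an ET-to-EPT switch that did not start from estrogen therapy.

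The planned quality control may not catch this. Section 9.8 has two researchers run the analysis independently and cross-check, but both would take the code list from the same Table 2.

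**Working it through.** **Inputs.** The code lists are in Table 2 (Section 9.3.1) and Table 4 (Section 9.3.2). The index-date rule is in Section 9.2. That ethynodiol diacetate is a progestin is general drug-class knowledge and is the one premise not stated in the protocol. The protocol gives no figure of its own to reproduce on this point.

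**Code counts.** Table 2 has 39 ET codes, 30 fixed-combination EPT codes, 9 daggered progestin codes and 1 tibolone code. Table 4 lists 18 transdermal codes, of which 16 are ET and 2 are EPT, and 12 transvaginal codes, all ET. Oral ET codes = 39 − 16 − 12 = 11. 156401ATB is in neither Table 4 list, so it is one of the 11.

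**Rules applied.** Norethisterone (203201ATB) is the comparator, and an oral estradiol valerate code (155001ATB) is the estrogen. The middle column reads class strictly by block.

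| On one prescription | As written, by block | Row moved to daggered progestins |
|---|---|---|
| 156401ATB alone | ET, oral, can set the index date | not MHT |
| 155001ATB + 156401ATB | ET | EPT |
| 203201ATB alone | not MHT | not MHT |
| 155001ATB + 203201ATB | EPT | EPT |

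The first and third rows show the inconsistency most plainly: two stand-alone progestins, treated in opposite ways. After the move, ET codes fall from 39 to 38 and oral ET codes from 11 to 10.

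**Direction of the effect on the quarterly ET share, if the name is right.** Under the corrected list, let T be the women with MHT in a quarter and E those with ET. Let L be the women who count as MHT in that quarter only because of this code on its own. Let A be the women already in T but not in E who gain an ET label through this code.

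- Corrected share = E/T.
- Share as written = (E + L + A)/(T + L).
- Difference = [L(T − E) + A·T] / [T(T + L)], which is zero or positive.

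The EPT share moves the other way. If F women have EPT under the corrected list, and P of them have it only through the estrogen-plus-156401ATB pair, it goes from F/T to (F − P)/(T + L). If the asterisk footnote governs the pair, P is zero and A contains only women with a separate lone prescription.

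The protocol gives none of L, A or P, so no number can be put on either difference. If all three are zero, so are the differences.

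**The case against.** **The name may be the error, not the class.** The protocol does not say what kind of drug ethynodiol diacetate is, and Table 2 contains misspelled ingredient names elsewhere. If 156401ATB denotes an estrogen, the class is correct, no woman is misclassified and the defect is a wrong label. This stands. The code number follows those of the estrogens (estropipate is 1555, this row is 1564), which is compatible with an ingredient name in that part of the alphabet but does not settle which one. The consequences are therefore conditional on the name being right.

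**The pair may already be EPT.** The asterisk footnote brings estrogen monotherapy plus progestin monotherapy into EPT and does not limit this to daggered ingredients. An analyst who recognises the drug as a progestin could class the pair as EPT under the text as it is. This also stands, and it makes the lone prescription the firmer consequence.

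**The reach is limited.** Only women aged 40-59 at cohort entry with a Table 1 diagnosis are eligible (Section 9.2.1), so use of the drug outside that group does not enter the cohort.

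A reader might infer three stronger claims, none of which the documents support:

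- *Every woman with this code has the wrong class.* A woman who also receives a true ET code in the period is ET either way. A woman with only a lone prescription is not wrongly classed within MHT; she should not be in MHT at all.
- *ET counts are overstated by the code's share of ET prescriptions.* Section 9.3.2 counts patients, and a prescription share does not convert to a patient share. Nor does the protocol anchor any such share; 1 of 39 codes says nothing about volume.
- *The class error drives all of Outcomes 3 to 6.* The age, symptom and route trends and the MPR contain no ET/EPT term. A spurious index date or cohort entry can reach them, but the class label itself does not.

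**Conclusion.** The row is internally inconsistent: a drug named as a progestin is classed as an estrogen and exempted from the rule for stand-alone progestins. Granted the drug class, one of the two entries must be wrong.

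If the name is right, a lone prescription in an eligible woman counts as oral ET and can set the index date, against the protocol's own dagger rule. The classification of an estrogen plus this code on one prescription is ambiguous: ET by block, EPT by one reading of the asterisk footnote. The effect runs through MHT membership (and so the prevalence figures in Outcomes 1 and 2), the index date, and the ET/EPT shares and switches. Its direction is to raise the ET share and lower the EPT share, or leave them unchanged. Its size cannot be computed from the documents and may be small or zero.

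If the name is wrong, only the label needs correcting. The point is worth settling because the check is cheap and the row feeds the definition of exposure, not because a material bias has been shown.

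**What to change.** Before the HIRA application (planned for 3Q 2023 in Section 6), check 156401ATB against the HIRA ingredient master.

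- If it is ethynodiol diacetate, move the row to the dagger-marked progestins in Table 2 and in the extraction code list. It then counts only with an estrogen on the same prescription, as EPT, and never alone.
- If the code denotes an estrogen, correct the ingredient name and leave the class as it is.

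The cost is one lookup and one edited row. No analysis method changes, and if the code turns out to have no prescriptions in the cohort, the results do not change either.
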